## 15.2 ANALYSIS OF THE SECONDARY OBJECTIVES

### 15.2.1 First Secondary Objective

The secondary objective '*To assess the relationship between reinjection intervals and drug effectiveness*' will be assessed considering the following outcomes:

- Re[injection interval in months defined for each reinjection in the study eye (see definition in Section 15.1)
- For effectiveness (in the study eye):
  - BCVA change (ETDRS letters) from the last assessment prior to Ozurdex injection to 7–12 weeks following each Ozurdex implant injection
  - BCVA change (ETDRS letters) from the last assessment prior to the first Ozurdex implant injection to 7-12 weeks following each Ozurdex implant injection
  - CRT by OCT change ( $\mu\text{m}$ ) from the last assessment prior to Ozurdex injection to 7-12 weeks following each Ozurdex implant injection
  - CRT by OCT change ( $\mu\text{m}$ ) from the last assessment prior to the first Ozurdex implant injection to 7-12 weeks following each Ozurdex implant injection

#### Description of drug effectiveness in the study eye

As preliminary description of drug effectiveness, BCVA in the study eye will be described at baseline and during the follow-up period using descriptive statistics for the following parameters:

- Last BCVA (ETDRS letters) prior to each Ozurdex injection [DV]
- BCVA (ETDRS letters) at 7-12 weeks following each Ozurdex injection,
- Change in BCVA (ETDRS letters) from baseline to 7-12 weeks following each Ozurdex injection [DV],
- Change in BCVA (ETDRS letters) from the value prior to Ozurdex reinjection to 7-12 weeks following each Ozurdex reinjection [DV].

Note: See the rule defined in Section 21.2 in case several measurements are available within the 7-12 week time window.

A similar description will be performed for CRT ( $\mu\text{m}$ ) in the study eye, regardless of the technology used for CRT measurement (confocal scanning laser ophthalmoscope; OCT; OCT – angiography; retinal thickness analyser; ultrasound).

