### 6.2 Outcome Variables

Ozurdex Real-word Utilization

- Number of Ozurdex implant injections per year
- Time between Ozurdex implants injections

Effectiveness:

- BCVA change from time of injection to 7-12 weeks following each Ozurdex implant injection
- BCVA change from time of first Ozurdex implant injection to 7-12 weeks following each Ozurdex implant injection
- CRT by OCT change from time of injection to 7-12 weeks following each Ozurdex implant injection
- CRT by OCT change from time of first Ozurdex implant injection to 7-12 weeks following each Ozurdex implant injection

Safety:

- Number and percentage of patients who experienced AESIs

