#### **10.8.2 Central Retinal Thickness**

CRT measured in the study eye will be collected at baseline and at all visits during the study period if it was measured using OCT. Technology and device brand used to measure OCT will also be collected.

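### SAP 15.2.1 describes CRT from any technology, including ultrasound, although both documents define the outcome as CRT by OCT; the departure is not declared in SAP Section 22

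*SAP*

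**What the plan says.** **Outcome.** Protocol 6.2 lists "CRT by OCT change from time of injection to 7-12 weeks following each Ozurdex implant injection", and a companion outcome measured from the first injection. SAP 15.2.1 repeats both in its outcome list, again as "CRT by OCT change".

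**Collection.** Protocol 10.8.2 has CRT in the study eye recorded at baseline and "at all visits during the study period if it was measured using OCT". It adds: "Technology and device brand used to measure OCT will also be collected".

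**Analysis.** Later in SAP 15.2.1, after the description of BCVA, comes this: "A similar description will be performed for CRT", to be done "regardless of the technology used for CRT measurement". The technologies named are "confocal scanning laser ophthalmoscope; OCT; OCT – angiography; retinal thickness analyser; ultrasound".

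**Reach.** SAP 15.2.3 applies the same description to patients naïve to anti-VEGF treatment and to those who are not. The part of SAP 15.2.1 on the relationship with the reinjection interval says only that CRT will be analysed like BCVA; it mentions no technology.

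**Declared changes.** SAP Section 22 lists two changes from the protocol: the reason for the initial injection and the contralateral eye. CRT technology is not among them.

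**The concern.** Within one SAP section the outcome is OCT-based and the description is not. Once a non-OCT value is in the database, the two statements cannot both be followed. A reader of the report would take the CRT results to be OCT results, because that is how the outcome is defined and Section 22 says nothing to the contrary.

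The numerical issue is that CRT is analysed as a within-eye change. If the value before an injection and the value 7-12 weeks after it come from different technologies, any systematic difference between them is counted as treatment change. The SAP handles mixed methods for BCVA by converting every value to approximate ETDRS letters (21.3.5). It has no comparable step for CRT and specifies no CRT analysis that uses the recorded technology or brand.

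At stake are the CRT summaries for the third secondary objective, where the pooled description is explicitly reused. The CRT part of the first secondary objective is affected too: its description pools explicitly, and its interval analysis leaves the matter open.

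**Working it through.** The plan gives no CRT figure to reproduce: its precision calculations concern the reinjection interval and BCVA only. The check is a comparison of texts, followed by an illustration on assumed inputs.

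**1. Does another rule restore the OCT restriction?**

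- Change derivation (SAP 21.3.5): the value at 7-12 weeks minus the last value before the injection, or before the first injection. There is no condition on technology.
- Several values in the window (SAP 21.2): they are averaged in µm. There is no condition on technology, so one post-injection value may blend two of them.
- Interval analysis (SAP 15.2.1): no technology is stated. The outcome list at the head of the section says OCT; the description that precedes this analysis says any technology.
- Naïve objective (SAP 15.2.3): refers back to the pooled description.
- Section 22: silent.

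The only safeguard is the collection rule in protocol 10.8.2. The SAP's list of five technologies provides for values that this rule would keep out.

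**2. How an offset enters a change.** Let each technology read the true thickness plus a constant. Then

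observed change = true change + (offset of the later technology − offset of the earlier one).

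The bracket is zero when both ends use the same technology. When they differ, it is the full offset d. If the window mean combines one OCT and one non-OCT value against an OCT starting value, it is d/2.

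**3. Effect on the mean.** Let p1 be the share of pairs that switch in one direction and p2 the share that switch back, with a common offset d:

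mean shift = (p1 − p2) × d.

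The documents give none of these inputs. The values below are assumptions.

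| Net share p1 − p2 | d (µm) | Shift (µm) |
|---|---|---|
| 0.05 | 30 | 0.05 × 30 = 1.5 |
| 0.10 | 50 | 0.10 × 50 = 5 |
| 0.20 | 100 | 0.20 × 100 = 20 |
| 0 (no non-OCT values) | any | 0 |

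**4. Balanced switching.** With p1 = p2 = 0.10 and d = 100 µm, the mean shift is (0.10 − 0.10) × 100 = 0. If switching is unrelated to the true change, the added variance is (p1 + p2) × d² = 0.20 × 100² = 2,000 µm². This noise would widen the confidence intervals and tend to weaken a correlation with the reinjection interval.

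**5. Rough scale.** Protocol 5.1 quotes a mean average CRT reduction of 111.6 µm in the sham-controlled phase III trials. The range above is 1.5/111.6 = 1.3% to 20/111.6 = 17.9% of it. That figure averages over three years and is not a 7-12 week change, so it gives an order of magnitude only.

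**The case against.** The strongest answer is that there may be nothing to pool. If sites follow the protocol and enter CRT only "if it was measured using OCT", the pooling clause is idle. A reader might infer from the SAP's list that ultrasound or scanning-laser values are in the data. The documents do not show this: the clause admits such values but does not establish that any exist. This stands, and it makes the harm conditional.

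Other stronger readings also go too far:

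- **That the SAP expressly pools technologies in the interval analysis.** The clause belongs to a description that the SAP calls preliminary. For the correlation and the median split, the point rests on the absence of a restated restriction. Only the reuse for the naïve objective is explicit.
- **That protocol 7.3.2 concedes this bias.** That section speaks of methods differing across sites and gives the OCT method as an example. A constant difference between sites cancels in a within-eye change. The section shows that measurement heterogeneity was recognised, not that eyes switch technology between measurements.
- **That the share of mixed pairs times the offset is the bias.** This is so only if all mixed pairs switch the same way. If the assumed 5-20% is read as the share of all mixed pairs, 1.5-20 µm is an upper bound.
- **That the main analysis must match device brand.** Neither document promises this, and changes of OCT brand fall within the protocol's own outcome. A brand condition would drop pairs, possibly not at random, from a naïve subgroup of up to 50 patients.

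It is also fair to say that CRT is a secondary outcome in a study without hypotheses, and that the naïve comparison is purely descriptive. This limits the weight of the point. It does not reconcile the two SAP statements or excuse the omission from Section 22.

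**Conclusion.** The point holds as an internal contradiction and an undeclared departure from the protocol. The outcome is CRT by OCT and collection is limited to OCT, yet the SAP's description admits four further named categories and Section 22 does not say so. That much rests on the text alone and is certain.

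The numerical consequence is possible but unquantified. It depends on the net share of pairs that switch technology in one direction and on the offset, neither of which the documents give. Under the assumed ranges the shift in mean change is 1.5-20 µm. It is nil if only OCT values were entered, and it is confined to added variance if switches balance. A claim that the CRT results are biased would go beyond the documents.

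The change is worth making before analysis. If there are no non-OCT values it costs nothing, and if there are some it is needed for the results to match the stated outcome.

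**What to change.** 1. In SAP 15.2.1 and 15.2.3, restrict the main CRT analyses, including the interval analysis, to OCT values at both ends of each change. Apply the same restriction before values in the 7-12 week window are averaged.
2. State whether OCT-angiography counts as OCT, since the SAP lists it separately, and how values with no recorded technology are treated.
3. Report the number of CRT values excluded by this rule.
4. Keep the all-technology analysis as a sensitivity analysis and list it in SAP Section 22.
5. Use the collected device brand for a further sensitivity analysis limited to same-brand pairs, not as a condition of the main analysis.

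The cost is SAP wording and a filter on a variable that the protocol already collects. The downside is that any pair with a non-OCT value at either end leaves the main analysis; the all-technology sensitivity analysis retains it.

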### Relationship between reinjection interval and drug effectiveness

The potential relationship between Ozurdex reinjection interval and BCVA will be assessed by considering, for each Ozurdex injection  $j$  ( $j \geq 1$ ) in the study eye, the time interval between injection  $j$  and injection  $(j+1)$  and BCVA change from the value prior to injection  $(j+1)$  to 7-12 weeks following injection  $(j+1)$ . All injections of the patient will be considered all together for this analysis.

As a first approach, a figure (scatter plot) defined by Ozurdex reinjection interval (in months) on the horizontal axis and BCVA change (in ETDRS letters) on the vertical axis will be plotted. A linear regression line along with the spearman rank coefficient and p-value will be superimposed on the data of the scatter plot.

As a second approach, the median Ozurdex reinjection interval will be calculated considering all reinjection intervals for a patient. BCVA change (in ETDRS letters) will be then summarized using descriptive statistics by reinjection intervals categorized in two classes according to the median ( $\leq$  median;  $>$  median). The 95% CI of the mean BCVA change will be provided in each class. Based on the observed distribution, other categories than the median may be considered to categorize the reinjection interval.

The same analysis will be performed considering, for each Ozurdex injection  $j$  ( $j \geq 2$ ) in the study eye, the time interval between injection  $j$  and injection  $(j+1)$  and BCVA change from the value prior to the first Ozurdex injection in the study eye (=baseline value) to 7-12 weeks following injection  $(j+1)$ .

A similar analysis will be performed to assess the potential relationship between reinjection interval and CRT in the study eye.

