#### **14.2.2.3.1 Relationship between Re[in]jection Intervals and Effectiveness**

Analysis will be performed considering each Ozurdex reinjection separately (second injection or first reinjection, third injection or second reinjection...) (see Figure 1).

Change in BCVA from time of reinjection to 7-12 weeks following reinjection and change in BCVA from time of first injection to 7-12 weeks following reinjection will be summarized for each reinjection. The same analyses will be performed for the change in CRT.

A first approach to assess the relationship between reinjections intervals and effectiveness will be to consider time interval between two injections (previous injection - reinjection) as a continuous parameter. The potential relationship between time interval and effectiveness will be assessed graphically using a scatter plot. Time interval between two injections (in months) will be plotted on the horizontal axis and either BCVA change or CRT change from time of reinjection to 7-12 weeks following reinjection will be plotted on the vertical axis. The corresponding correlation coefficients will be calculated. The same scatter plot will be done for the change in BCVA and CRT from time of first implant injection to 7-12 weeks following each Ozurdex implant injection.

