### Sites and study population

Site selection will aim to recruit qualified ophthalmologists experienced in intravitreal injections who are most likely to treat patients with DME with Ozurdex. A sample of ophthalmologists working in experienced medical retinal centers treating DME patients will thereby be selected.

From a public health and market access perspective, the present study population constitutes a broader real-world patient population than that reflected in clinical trials. The present study design cannot make any conclusions on causal relationships, but can rather explore real-world Ozurdex drug utilization patterns, effectiveness and safety. It is expected that the results from this study may be generalizable to the overall population presenting with DME and treated with Ozurdex in Germany and Switzerland.

Patients may contribute at most one eye into the study. If both eyes meet the inclusion and exclusion criteria, the eye that received the most Ozurdex injections will be chosen as the study eye.

Inclusion criteria are:

1. Patient received at least two Ozurdex implants in the study eye to treat visual impairment due to DME

2. Male or female patient aged  $\geq 18$  years at time of first Ozurdex implant injection in the study eye
3. First Ozurdex implant injection in the study eye occurred after 1 January 2015
4. Patient was followed-up at the site for at least 12 months after the first Ozurdex implant injection in the study eye

Exclusion criterion is:

1. Patient received Ozurdex implants in the study eye as part or during a clinical study

[REDACTED]

[REDACTED]

[REDACTED]

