#### **15.2.2 Second Secondary Objective**

The secondary objective '*To describe the reasons for reinjection*' will be assessed considering the primary reason for injection (Disease progression, Lack of effect, Other) reported at each follow-up visit at which an Ozurdex injection was performed in the study eye. The analysis will be summarized using descriptive statistics.

For the study eye, the primary reason for injection (Disease progression, Lack of effect, Other) will be first summarized for each reinjection (i.e. first reinjection, second reinjection, etc.). Then, the primary reason for injection will be described considering all reinjections (the denominator for percentages will be the total number of reinjections in the study eye). Reasons reported as free texts in the 'Other' category will be summarized in a listing.

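### The pooled interval–effect correlation mixes between-eye and within-eye association and carries a p-value that treats repeated points from one eye as independent

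*SAP*

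**What the plan says.** SAP 15.2.1 (Relationship between reinjection interval and drug effectiveness) makes each reinjection one point: the interval before it, paired with the BCVA change from just before that injection to the 7–12 week window after it. On pooling it says: "All injections of the patient will be considered all together for this analysis". The output is specified as: "A linear regression line along with the spearman rank coefficient and p-value will be superimposed on the data of the scatter plot". A second approach divides the intervals at the median, and: "The 95% CI of the mean BCVA change will be provided in each class". (I take this as one cut-point across all intervals, although the sentence defining the median could be read as a median per patient.) The same steps are repeated for change from baseline and for CRT.

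Protocol 14.2.2.3.1 differs. It says "Analysis will be performed considering each Ozurdex reinjection separately", and asks for less: "The corresponding correlation coefficients will be calculated". It mentions neither pooling nor a p-value, and SAP 22.0 does not list either as a change.

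On structure: "Patients may contribute at most one eye into the study", so patient and study eye are the same cluster. Eligibility includes: "Patient received at least two Ozurdex implants in the study eye to treat visual impairment due to DME". An eye may thus supply only one interval. SAP 15.2.2 separately tabulates the "primary reason for injection (Disease progression, Lack of effect, Other) reported at each follow-up visit" at which an injection was given. The interval–effect analysis does not use it.

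**The concern.** Reinjection timing in routine care is not assigned. Two of the three pre-listed reasons, disease progression and lack of effect, describe how the eye is doing, so the plan itself allows for timing that follows response. A lasting trait of the eye could then affect both axes of the plot, and the pooled coefficient would pick up that trait as well as any effect of interval length.

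Nothing elsewhere in the plan separates the two. The Table 6-1 subgroups (country, prior anti-VEGF treatment, lens status, concomitant treatment) do not remove differences in responsiveness. The confounding paragraphs (Protocol 7.3.3, SAP 7.0) deal only with safety events. The change-from-baseline version is more exposed, because all points of one eye share a single baseline value (SAP 21.3.5).

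At stake is the first secondary objective. A fitted line with a small p-value would be read as information on interval length, whatever its source.

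**Working it through.** **The plan's own figure.** The documents give no figure for the correlation. The nearest is the precision of the mean interval (SAP 19.0), ω = 1.96 × SD/√n with n = 150:
- SD 1.5: 1.96 × 1.5/√150 = 0.240 months
- SD 3.0: 1.96 × 3.0/√150 = 0.480 months

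These round to the stated 0.2 and 0.5. The calculation concerns a mean and offers no support for the correlation or its p-value.

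**Set-up with no effect of interval within an eye.** Let *s* be the share of variance lying between eyes (same for interval and BCVA change) and ρ the correlation between an eye's usual interval and its usual response. Neither is in the documents; both are assumptions. The expected pooled correlation is r = ρ × s, and on the rank scale r_S = (6/π) arcsin(r/2). Ignoring clustering, the test statistic is about r_S × √(n − 1).

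Further assumptions: 150 eyes (SAP 19.0), follow-up 12 to 44 months, interval 5.5 (SD 1.8) months, half of the pairs evaluable, giving about 315 points. With s = 0.2 and √314 = 17.72:

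| ρ | r = 0.2ρ | r_S | z = 17.72 r_S | approximate P(p<0.05) | simulated mean r_S | simulated P(p<0.05) |
|---|---|---|---|---|---|---|
| 0.3 | 0.06 | 0.057 | 1.02 | 17% | 0.06 | 20% |
| 0.5 | 0.10 | 0.096 | 1.69 | 39% | 0.09 | 38% |
| 1 | 0.20 | 0.191 | 3.39 | 92% | 0.19 | 92% |

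Formula and simulation agree.

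**Clustering alone.** At ρ = 0 the coefficient is unbiased, but the p-value still rejects in 5% to 14% of studies for s from 0.2 to 0.5, because points from one eye are not independent.

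**A second set of assumptions.** Interval 6.0 (SD 2.3) months, the SD being that of the cited 27-patient study; BCVA-change SD 10 letters, the upper value in SAP Table 18-2; s = 0.3 or 0.5; all pairs evaluable; follow-up 8–16, 12–24 or 12–44 months (about 210, 350 or 620 points). The shortest range allows for SAP 21.2 ending follow-up at the first concomitant anti-VEGF or corticosteroid treatment.

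| ρ | mean Spearman | p<0.05 | pooled slope, letters/month | above minus at-or-below median, letters |
|---|---|---|---|---|
| −0.5 | −0.14 to −0.26 | 61–99.7% | about −0.7 to −1.2 | about −2.4 to −4.3 |
| 0 | about 0 | 5–18% | about 0 | about 0 |
| +0.5 | +0.14 to +0.26 | 63–99.5% | +0.7 to +1.2 | +2.4 to +4.4 |

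The median split shows the same fault. Between 12% and 53% of the interval variation lay within eyes, so the pooled statistic really is a mixture. A within-eye slope stayed between −0.04 and +0.04 letters/month and rejected in about 5–8%.

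**Limit of the within-eye slope.** That good behaviour assumes that response to one implant does not affect the next interval. With ρ = 0, s = 0.2, no true effect, and a correlation of 0.3 to 0.5 between a response and the following interval, the within-eye slope is about −0.3 to −1.0 letters/month and rejects in about 14% to 35% of studies. The pooled Spearman then stays near 0 and rejects in about 6%.

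**The case against.** The strongest defence is that the plan is exploratory. The protocol rests on no hypothesis (Section 6), both documents disclaim causal conclusions, and the SAP speaks only of a potential relationship. That stands as a reason to keep the plot and coefficient. It does not rescue the p-value: a test that ignores clustering is not made valid by a disclaimer, and for its naïve-versus-pretreated comparison the SAP itself rules out tests (15.2.3).

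A reader might infer something stronger: that the analysis compares different eyes only, and so makes long intervals look more effective. The documents do not support this. The SAP pools all reinjections, so eyes with several contribute within-eye information too; only the protocol's separate analyses and single-reinjection eyes are purely between-eye. Nor is the direction known. The reason categories come without frequencies and without any link to later gain. An eye reinjected early because its vision fell has more room to gain, and an eye with a strong but short-lived response would also reverse the sign. For CRT, benefit is a negative change, so signs flip again.

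It is also fair to object that the 92% needs one trait driving both axes perfectly, and that the within-eye slope has a bias of its own. Both objections stand and shape the fix.

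**Conclusion.** The point holds in this form: the planned analysis does not separate between-eye from within-eye association, and its p-value treats repeated points per eye as independent. It can therefore show a relationship when interval length has no effect. At a between-eye share of 0.2 and 12 to 44 months of follow-up, the false-positive frequency runs from about 20% (ρ = 0.3) to 92% (ρ = 1); with ρ = 0 it is 5% to 14% for shares of 0.2 to 0.5. The shares, ρ, the evaluable fraction and the distribution of follow-up are assumptions. The documents fix neither the size nor the direction.

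A reader might also infer that the within-eye slope is the correct answer to the objective. That goes too far: the plan's own reason categories leave room for the feedback from response to next interval that biases it.

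**What to change.** In SAP 15.2.1:

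1. Keep the scatter plot, regression line and Spearman coefficient as description, labelled as mixing between-eye and within-eye association. Remove the p-value.
2. Add, for BCVA and CRT, a model with a patient random intercept and two interval terms: the patient's mean interval and each interval's deviation from that mean. Report both slopes with cluster-robust 95% CIs, and the number of eyes with at least two evaluable reinjections.
3. Give the median-split classes the same label and patient-clustered CIs.
4. State that neither slope is the effect of interval: the between-eye slope is open to confounding by responsiveness, and the within-eye slope is biased if response to one implant affects the next interval.
5. List the move from separate to pooled reinjections in SAP 22.0.

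The cost is SAP wording and one standard model per outcome on pairs already derived. The within-eye CI will be wider, because eyes with one evaluable interval do not inform it. With half of the pairs evaluable and 12 to 44 months of follow-up, about 94 of 150 eyes would have more than one; shorter follow-up leaves fewer.

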**Figure 1 Example of Reinjections Intervals and Effectiveness Outcomes Disposition in a Hypothetic Patient**

BCVA=Best corrected visual acuity; CRT=Central retinal thickness

- Last BCVA and CRT measured before injection of Ozurdex
- BCVA and CRT measured 7 to 12 weeks following each reinjection

For "Time interval 1", BCVA and CRT change from measurement 1 to measurement 2 will be considered; for "Time interval 2" BCVA and CRT change from measurement 3 to measurement 4 will be considered; and for "Time interval 3", BCVA and CRT change from measurement 5 to measurement 6 will be considered.

A second approach will be to consider time interval between two injections as a categorical variable; either 2 categories will be considered based on median time interval or other categories will be considered based on observed distribution. BCVA change and CRT change from reinjection to 7-12 weeks following reinjection and BCVA and CRT change from time of first implant injection to 7-12 weeks following each Ozurdex implant injection will be described by these categories.

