## **15.0 ANALYSES OF THE OBJECTIVES OF THE STUDY**

### **15.1 ANALYSIS OF THE PRIMARY OBJECTIVE**

The primary objective '*To assess reinjection interval of Ozurdex implants in patients with DME in real-world in Germany and Switzerland*' will be assessed by the following outcomes:

- Total number of Ozurdex reinjections in the study eye during follow-up, and considering years after the first Ozurdex injection in the study eye (See definition in Table 21-1).
- Re[injection interval defined in months as: (Date of injection (j+1) – Date of injection j) ÷ (365.25÷12), for j=1,...,n where n is the number of reinjections in the study eye. The result will be rounded to 0.1.

The number of Ozurdex reinjections in the study eye per year will be first summarized using descriptive statistics for the following parameters:

- The total number and percentage of Ozurdex reinjections received during follow-up.
- Number and percentage (with 95% CI) of patients with at least one Ozurdex reinjection during Year 1 (See definition in Table 21-1), and number of reinjections per patient during Year 1, for all patients in the analysis population. Note: the first Ozurdex injection will not be considered here, only reinjections will be counted.
- Number and percentage (with 95% CI) of patients with at least one Ozurdex reinjection and number of reinjections per patient during Year k (k=2, 3), for patients having a complete Year k of follow-up (see definition of 'Complete year' in Section 21.2).
- Number and percentage of patients receiving each Ozurdex reinjection (first, second, third, etc) for each year of follow-up (Year k, k=1 to 3) considering patients having the complete year of follow-up.

The Ozurdex reinjection interval in the study eye will be described using descriptive statistics for the following parameters:

- Re[injection interval (months) considering all eligible reinjections recorded in the EDC. The 95% CI of the mean will also be presented.
- Re[injection interval (months) considering each reinjection separately (i.e. first reinjection, second reinjection, etc). 95% CI of the mean will also be presented.

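### SAP 15.2.1 words the median reinjection interval as a patient's own median; split at that cut-off, the two classes would not separate short from long intervals

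*SAP*

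**What the plan says.** The first secondary objective is approached in two ways in SAP Section 15.2.1. The first is a scatter plot with a regression line and a Spearman coefficient. The second is a two-class comparison. For that one, "the median Ozurdex reinjection interval will be calculated considering all reinjection intervals for a patient", and the change in BCVA is then summarised "by reinjection intervals categorized in two classes according to the median", with a 95% CI for the mean change in each class. An option follows: "Based on the observed distribution, other categories than the median may be considered to categorize the reinjection interval".

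The opening paragraph of the same subsection adds "All injections of the patient will be considered all together for this analysis". The analysis is run for BCVA and repeated for CRT. It covers change from the value before the reinjection (j ≥ 1) and change from baseline (j ≥ 2). Table 6-1 schedules subgroup analyses for this objective.

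The protocol, in Section 14.2.2.3.1 after Figure 1, says that "either 2 categories will be considered based on median time interval or other categories will be considered based on observed distribution". It attaches no patient qualifier to the median, and neither does its synopsis. SAP Section 22, which lists changes from the protocol analyses, does not mention this one.

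**The concern.** The only median the subsection defines is one taken over the intervals of a patient, so the later reference to the median points back to it. A programmer following the text would compute one median per patient and compare each interval with it.

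The two classes would then separate a patient's shorter intervals from that same patient's longer ones. They would not separate short intervals from long ones across the study. A nine-month interval could sit in the lower class while a five-month interval from someone else sat in the upper class. Readers would still take the two class means and their CIs as early versus late reinjection, and a real relationship with interval length would be diluted.

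Nothing else in the SAP settles the matter. Section 21.3 says it holds the derivation of all derived variables, but it defines neither this median nor the interval class. Where the SAP clearly pools over the study, it uses different words: Section 15.1 refers to every eligible reinjection in the EDC, and Section 15.2.2 uses the total number of reinjections as denominator.

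**Working it through.** The plan states no figure for this split, so there is none to reproduce. The check has three parts.

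**1. Counts under the literal rule.** Inclusion criterion 1 is "Patient received at least two Ozurdex implants in the study eye to treat visual impairment due to DME", so two implants suffice. Section 15.1 defines one interval per reinjection, "where n is the number of reinjections in the study eye", so two implants give one interval. With k distinct intervals, the numbers at or below / above the patient's own median are:

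- k = 1: 1 / 0
- k = 2: 1 / 1
- k = 3: 2 / 1
- k = 4: 2 / 2
- k = 5: 3 / 2

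A single interval equals its own median and goes to the lower class whatever its length. Every odd k adds one extra interval to the lower class. The k = 1 effect exists only where j starts at 1. The change-from-baseline analysis starts at j = 2, so a two-implant patient contributes nothing to it.

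**2. Worked example (invented intervals, months).** Four patients: {9.0}, {4.0, 5.0}, {7.0, 8.0, 10.0}, {3.8}. Their own medians are 9.0, 4.5, 8.0 and 3.8.

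- Own-median split: lower class 9.0, 4.0, 7.0, 8.0, 3.8 (mean 31.8/5 = 6.36); upper class 5.0, 10.0 (mean 7.50). Gap 1.14.
- Pooled median 7.0: lower class 3.8, 4.0, 5.0, 7.0 (mean 19.8/4 = 4.95); upper class 8.0, 9.0, 10.0 (mean 9.00). Gap 4.05.

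Three of the seven intervals (9.0, 8.0 and 5.0) change class.

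**3. Illustrative simulation.** The following are assumptions, because the documents do not give them: mean interval 6 months, between-patient SD 1.0 to 2.5, within-patient SD 1.0 to 2.0, follow-up uniform from 12 to 44 months, minimum interval 2 months; 20,000 patients per setting. The corners of that range give:

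| Between / within SD | Classed differently | Gap, pooled median | Gap, own median |
|---|---|---|---|
| 1.0 / 1.0 | 31% | 2.28 | 1.28 |
| 1.0 / 2.0 | 24% | 3.46 | 2.49 |
| 2.5 / 1.0 | 38% | 3.95 | 1.43 |
| 2.5 / 2.0 | 31% | 4.43 | 2.34 |

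Settings inside the range agree; the lowest own-median gap found was 1.24. As a check on the first row, a normal distribution split at its median has a gap of 2 × √(2/π) × SD = 1.596 × SD, and 1.596 × √(1.0² + 1.0²) = 2.26 against 2.28 simulated. Total SD runs from 1.41 to √(2.5² + 2.0²) = 3.20, slightly wider than the 1.5 to 3.0 in SAP Section 19.

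Patients with a single interval make up only 3% to 7% of patients here and about 1% of intervals.

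**Sensitivity.** A second simulation used the planned 150 patients, a mean of 5.5 months and SDs of 1.5, 2.3 and 3.0. It assumed that 20% to 70% of patients have exactly two implants and that the within-patient correlation is 0 to 0.6. Then 24% to 42% of intervals are classed differently, and 60% to 80% fall in the lower class. At SD 2.3 the gap is about 1.2 to 2.7 months, against about 3.6 with a pooled median.

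**The case against.** The strongest reply is that one common cut-off was meant. The SAP never says that an interval is compared with its own patient's median; it speaks of the median in the singular. The option of other categories rests on the observed distribution, most naturally the study-wide one. The protocol analysed each reinjection separately, and the SAP sentence may only be saying that all of a patient's intervals now enter together. Section 22 is also what one would expect if no change of cut-off was intended. This stands as an account of probable intent. It does not make the wording safe, because the sentence that defines the median still says it is for a patient.

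The second reply concerns weight. The protocol states no hypothesis, and the class comparison gives means and CIs without a test. The scatter plot, regression line and Spearman coefficient use the interval as a continuous variable and do not depend on the cut-off. Nor does the primary objective. All of that stands and limits the severity. The freedom to choose other categories helps less: it is optional, applies after the distribution is seen, and leaves the default rule unchanged.

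A reader might also infer that two-implant patients are piled into the lower class throughout. The documents do not support that. It cannot occur in the change-from-baseline analysis. In the other analysis it needs a value in the 7–12 week window, and its weight depends on a share of two-implant patients that the documents do not give.

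**Conclusion.** The concern holds as a defect of wording with a real consequence if followed. Taken literally, Section 15.2.1 sets a patient-specific cut-off, departs from the protocol without declaring it, and produces classes that mix short and long intervals. Both change definitions and both outcomes are exposed to the mixing. The forced placement of two-implant patients affects the j ≥ 1 analysis only.

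The direction follows from the counting and does not depend on the simulation. The size does: about 24% to 38% of intervals classed differently, and a gap between classes of about 1.3–2.5 months in place of about 2.3–4.4, under assumed interval variability and follow-up.

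The text does not support the stronger conclusion that the SAP has settled on own-patient medians, or that the first secondary objective cannot be assessed. Severity is moderate: the comparison is descriptive, and the continuous approach to the same objective is intact.

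**What to change.** Replace the sentence that defines the median with: *For each analysis (j ≥ 1 and j ≥ 2), the median will be calculated once over all reinjection intervals of all Analysis Population patients contributing to that analysis; this single cut-off will classify every interval, and the same cut-off will be used in the subgroup analyses.*

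The median is specified per analysis because the j ≥ 2 set omits each patient's first interval and can have a different median. Holding the cut-off fixed across subgroups gives the classes the same meaning in each of them.

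The cost is one sentence in the SAP before programming. It needs no new data and adds no analysis. If a patient-specific cut-off was in fact intended, the SAP should say so, justify it and list it in Section 22.
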